Project Title: Once Daily versus Twice Daily Iron Supplementation to Treat Anemia in Pregnancy: A Prospective, Randomized, Placebo Controlled, Double Blinded, Clinical Trial

IRB#: 2004638

Version 8, September 24, 2019

Principle Investigator:

[name]

Assistant Professor, Department of Obstetrics and Gynecology
[name]

Summary

Anemia is a common problem in pregnancy, affecting as many as 1/4 of pregnancies in the developed world in the absence of iron supplementation. It is defined as a maternal hemoglobin (Hgb) less than 11mg/dL in the 1st or 3rd trimester and Hgb less than 10.5mg/dL in the 2nd trimester [1].. Anemia is associated with low birth weight, preterm birth, and increased risk for transfusion at the time of delivery [1]. The most common cause of anemia in pregnancy is iron deficiency. Iron deficiency anemia in pregnancy is typically treated with oral iron supplementation in the form of once or twice daily ferrous sulfate, which contains 65mg of elemental iron.

Iron balance is complex, and iron demands are increased in pregnancy. The fetus, placenta, and increased maternal red blood cell volume require about 1g of additional iron during the entire pregnancy. The average American diet contains only about 15mg of elemental iron, which is insufficient to meet this need[1]. It is recommended that pregnant women consume about double this amount during pregnancy[1].

The absorption of oral iron is low, ranging from 2-28%. Taking iron without food increases absorption. Hepcidin is a key regulator of iron absorption in mammals, increasing hepcidin decreases iron absorption. Hepcidin is increased with morning fasting dosing, which may affect the efficacy of twice daily dosing (Morretti). Well-designed clinical trials describing the optimal dosing for iron to treat anemia in pregnancy are limited [2, 3].

A recent publication by Morretti et al [4] evaluated the effect of different doses of oral iron in non-pregnant iron deficient young women. They evaluated the effect of varying doses of daily ferrous sulfate and once and twice daily dosing of ferrous sulfate on hepcidin levels and fractional and total iron absorption. Women were treated with a single daily dose ranging from 40-240mg of elemental iron. This 6-fold increase in elemental iron dosage only resulted in a 3 fold increase in the amount of elemental iron absorbed, contradicting the notion that more iron is better. In a second arm of the study, women were treated with twice daily dosing for a total of 180mg of elemental iron. **The results of the study demonstrated that 24 hours after a dose > 60mg, hepcidin increased and fractional iron absorption decreased by 35-45%. Multiple daily doses did not increase iron absorption beyond single daily dosing.** The authors concluded that providing daily dosages less than 80mg of elemental iron and avoiding

twice daily dosing maximized iron absorption. **The results of the study by Morretti et al challenge the conventional wisdom that more severe iron deficiency anemia in pregnancy is best treated by increasing from daily to twice daily supplementation. Morretti et al also did not evaluate for gastrointestinal side effects or increase in hemoglobin.**

Given the high incidence of iron deficiency anemia in pregnancy and the associated complications, we propose a prospective, randomized double blinded clinical trial to evaluate the optimal dosing of oral iron supplementation in pregnancy. We will recruit mothers identified as having iron deficiency anemia at the time of routine prenatal blood work in the second trimester. These subjects will be randomized to daily or twice daily ferrous sulfate 325mg (65mg of elemental iron). The primary outcomes will be hemoglobin concentration at the time of admission for delivery and post-partum and assessment of gastrointestinal side effects. The secondary outcome will be frequency of blood transfusion at the time of delivery.

Hypothesis: Once daily dosing of ferrous sulfate 325mg/dL will be associated with increased maternal hemoglobin concentration at the time of delivery and post-partum and decreased gastrointestinal side effects.

Specific Aims

1. Determine whether once daily dosing of oral iron is more effective in raising maternal Hgb concentration than twice daily dosing.
2. Determine whether once daily dosing of ferrous sulfate 325mg has a lower side effect profile than twice daily dosing.
3. Determine the relationship between frequency of maternal iron administration and maternal hepcidin
4. Determine the relationship between frequency of maternal iron administration and fetal iron stores

Secondary Aim

Determine whether once daily dosing of ferrous sulfate 325mg is associated with a lower rate of maternal blood transfusion at the time of delivery than twice daily dosing.

Inclusion Criteria

Singleton gestation in the second trimester (14-28 weeks) who is not on iron therapy and has a normal hemoglobin electrophoresis if from a high risk group for hemoglobinopathy.

Exclusion Criteria

Multiple gestation, maternal hemoglobinopathy or hemochromatosis, subjects with irritable bowel disease or irritable bowel syndrome, history of bariatric surgery or extensive bowel surgery, or individuals already receiving iron supplementation aside from prenatal vitamins.

Study Design

[figure not shown]
This will be a prospective, randomized, double blinded placebo controlled clinical trial. Subjects will be identified for possible enrollment during the second trimester during routine prenatal care. Criteria for enrollment will be a singleton intrauterine gestation as above. Subjects without anemia will have weekly questionnaires regarding GI symptoms during otherwise scheduled prenatal visits. Subjects with iron deficiency anemia as diagnosed by an Hgb concentration of less than 10.5-11mg/dL per ACOG guidelines and a ferritin of less than 15mg/dL will be randomized to once or twice daily iron supplementation by means of a computer generated random number list by the investigational drug pharmacy. The study drug will be provided by the University of Missouri Investigational Drug Pharmacy under the guidance of [name], the Investigational Drug Pharmacist for the University. Iron supplementation will be in the form of ferrous sulfate 325mg (65mg of elemental iron) once or twice daily. Anemic subjects will receive identical packs of drug with instructions to take one pill BID (twice daily). The morning pill will be ferrous sulfate 325mg. The evening pill will be randomized to contain either ferrous sulfate 325mg or placebo. The placebo will be produced by the investigational drug pharmacy and contain cellulose, a biologically inert plant fiber. The subjects and investigators will be blinded to assignment. As part of standard Obstetric care, the subject will have a hemoglobin repeated at the time of admission to labor and delivery and on post-partum day 1. Subjects who are not anemic will serve as controls and not receive a prescription. This is appropriate as the standard of care is not to treat non-anemic women with iron supplementation.

In addition to routine standard of care blood draws, subjects will have two extra samples of blood taken for research use at no cost to them. The first will be drawn at the time of enrollment, generally at the time of a clinically indicated blood draw for routine prenatal labs. The second will be drawn at the time of admission to the hospital for delivery or on post partum day 1, again generally at the time of an otherwise clinically indicated blood draw. At this time, a separate tube of about 10mL will be drawn for research purposes only. A sample of cord blood from the placenta will be obtained following delivery of the neonate as well. These samples will be stored for analysis of hepcidin and ferritin at the conclusion of the study. These values will be for research use only and will not be used in clinical care.

Subjects will be administered a validated questionnaire regarding gastrointestinal (GI) symptoms of iron usage at the time of follow up clinic visits [5]. This questionnaire will be administered via RedCap or via paper per patient preference. Compliance will be monitored by having the patient bring pill packs to her clinic visits.

Whether or not the patient required a blood transfusion in the peripartum period will be recorded. Due to the relative infrequency of this outcome, this will be evaluated as a planned secondary outcome with the understanding that the trial will not be powered specifically for this outcome.

All samples collected will be collected for, stored, and processed by the MU Biorepository. Following study related analysis, the MU Biorepository will de-identify what is left of the samples and store the excess for future non-specified research endeavors.

Risks and Benefits

1. Iron therapy is associated with mild gastrointestinal symptoms (upset stomach and diarrhea). Increased iron dosage may be associated with an increased risk of these symptoms. Significant gastrointestinal symptoms are rare with once or twice daily iron dosage. The additional iron in maternal diet (which is classically iron poor in the US) or in prenatal vitamins will not pose any additional maternal risk. There is no fetal risk to this study.
2. There are no individual benefits to enrollment in the study.

Subject withdrawal criteria and procedures specifying

- When and how to withdraw subjects from the trial / investigational product treatment.
If subjects are not compliant with the tasks required in the protocol.
- The type and timing of the data to be collected for withdrawn subjects.
All data collected from a withdrawn subject will immediately be destroyed.
- Whether and how subjects are to be replaced.
To replace withdrawn subjects, we will recruit another pregnant mother
- The follow-up for subjects withdrawn from investigational product treatment/trial treatment.
There will be no follow-up.

Data handling:

All data will be coded with an ID number. The key containing the ID numbers will be kept in a locked file separate from the data. Data generated from samples tested for this study will be stored by the MU Biorepository and by the research staff. . The data will be kept for 7 years after study completion. This data will not be shared with outside investigators or used for research other than this study. Additionally, data from this study will be included in the Prospective Obstetric Database (PODS) study for future use in de-identified fashion.

Data Analysis

Statistical Analysis: Statistical analyses will be performed using the IBM SPSS statistical software version 22 (IBM Corporation, Armonk, NY, USA). ANOVA will be used to assess the difference in mean hemoglobin at the time of admission and post-partum in the three arms for the study. Regression analysis will be used to explore the relationships of iron supplementation on maternal hemoglobin at delivery and fetal hemoglobin, hepcidin, and ferritin while controlling for maternal ferritin and hepcidin at enrollment. A planned secondary analysis will be to use a Chi-square or Fisher's exact test as appropriate to examine the incidence of blood transfusion during the admission for delivery. Significance will be set at $P \leq 0.05$.

Power Analysis: The mean hemoglobin concentration in pregnancy is about 12mg/dL and the standard deviation is about 1mg/dL. At an alpha of 0.05 a sample size of 17 subjects in each arm would be required to have 80% power to detect a difference of 1mg/dL in maternal hemoglobin. In order to account for subjects lost to follow up due to delivery at other facilities, transfer of care and a 20% lost to follow up rate, we will continuously enroll subjects until 50 subjects are randomized to treatment in order to preserve adequate power to assess our primary outcomes and control for covariates in the setting of lost to follow up. The prevalence of anemia in pregnancy is reported to be between 8 and 27% in the second and third trimesters of pregnancy[1]. As such, we anticipate a total sample size of around 250 (50 subjects on treatment divided equally between once and twice daily iron and 200 controls receiving routine prenatal care. Our facility delivers around 2000 patients per year, most of whom receive care in our clinics. As such, we anticipate being able to recruit our target sample size, including accounting for patient drop out and replacement, in 12-18 months. Based on prior published data [5], 10 subjects per arm are required to identify a difference gastrointestinal symptoms.

Anticipated results and future directions

Based on the increased hepcidin and reduced fractional absorption seen with multiple daily dosing, I anticipate that once daily dosing will be superior to twice daily dosing in

the treatment of anemia diagnosed during the second trimester of pregnancy. In this case, I plan a follow up study to evaluate once versus twice daily dosing in anemia diagnosed in the first trimester (1-14 weeks gestation), which is less common but may represent a more severe depletion of iron stores. **If twice daily dosing is proven to be equivalent or superior to once daily dosing in pregnancy, I plan a study similar to that of Morretti to determine if the changes in hepcidin levels seen with multiple daily doses of iron in the non-pregnant patient are also seen in pregnancy. It is possible that pregnant women have a less robust increase in hepcidin in response to oral iron and can benefit from increasing dosage. It is also possible that they would have a more robust response and would be better served with less frequent (i.e.) every other day dosing.** I plan to use preliminary data from this study to apply for external funds to answer these questions.

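### Aim 1 has two primary hemoglobin results and no rule for which one decides it, and the planned three-arm ANOVA does not isolate once versus twice daily dosing

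*Combined protocol and SAP*

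**What the plan says.** The Summary names the primary outcomes: "The primary outcomes will be hemoglobin concentration at the time of admission for delivery and post-partum and assessment of gastrointestinal side effects". The Study Design section shows that the two hemoglobin values are separate measurements: "hemoglobin repeated at the time of admission to labor and delivery and on post-partum day 1".

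The Hypothesis predicts that once daily dosing brings "increased maternal hemoglobin concentration at the time of delivery and post-partum and decreased gastrointestinal side effects", all in one sentence. The Specific Aims separate the questions. Aim 1 asks which schedule raises maternal hemoglobin more and gives no time point. Aim 2 is to "Determine whether once daily dosing of ferrous sulfate 325mg has a lower side effect profile than twice daily dosing".

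The Statistical Analysis section uses ANOVA for the "difference in mean hemoglobin at the time of admission and post-partum in the three arms". The third arm is the untreated, non-anemic control group. No follow-up contrast between the randomized arms is named. A regression is also planned, with the mother's hemoglobin around delivery as an outcome. One general threshold applies: "Significance will be set at" P ≤ 0.05.

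The Power Analysis reads "At an alpha of 0.05 a sample size of 17 subjects in each arm", for 80% power to detect a difference of 1 with standard deviation (SD) about 1. It names no time point. It raises enrollment to 50 randomized "in order to preserve adequate power to assess our primary outcomes", with 20% loss to follow-up. It gives GI symptoms a separate requirement of 10 per arm.

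**The concern.** A plan with several primary results needs to say which of them answers each aim. Here Aim 1 can be answered by admission hemoglobin, by post-partum hemoglobin, or by both, and each is tested at the full 0.05. If the two disagree, the deciding one can be chosen after the data are seen, and the error rate for Aim 1 is then no longer 5%.

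The planned test adds a second problem. Aim 1 compares the two randomized arms, but an overall three-arm ANOVA asks whether any of three means differ. One of the three groups was selected for not being anemic. A significant result therefore need not say anything about dosing frequency.

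**Working it through.** **Inputs.** From the Power Analysis: difference 1, SD 1 (in the plan's unit), alpha 0.05, power 80%, 17 per arm, 20% loss, 50 randomized in two equal arms (25 each), about 200 controls. Assumed, because the plan does not give it: the correlation between the two hemoglobin tests, taken as 0.5 to 0.9.

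**Step 1: reproduce the 17.** A two-sided, two-sample t test with difference/SD = 1 needs 16.7 per arm, rounded up to 17; power at 17 is 80.7%. A one-sided test would need 14. A three-arm ANOVA would need 16 per arm for means 0, 0, 1 and 21 for means 0, 0.5, 1. The stated figure therefore matches one two-sided, two-arm comparison at the full 0.05. Allowing for 20% loss, 17/0.8 = 21.25, so 22 per arm or 44 in total. The planned 25 per arm leaves 25 × 0.8 = 20 evaluable.

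**Step 2: false-positive error if either hemoglobin can decide Aim 1.** With no true difference, the error is 1 − P(|Z1| < 1.96 and |Z2| < 1.96), where Z1 and Z2 are bivariate normal with the assumed correlation.

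| Correlation | At least one hemoglobin test significant |
|---|---|
| 0 | 9.75% (1 − 0.95²) |
| 0.5 | 9.1% |
| 0.7 | 8.3% |
| 0.8 | 7.8% |
| 0.9 | 7.0% |

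Simulated t tests with 20 per arm agree with these to about 0.1 percentage point. The figures describe two-arm tests of once versus twice daily, not the three-arm ANOVA.

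**Step 3: power if both hemoglobin tests must succeed.** Each is at 0.05, with a true difference of 1 and SD 1 at both times. This rule does not inflate the false-positive error.

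| Evaluable per arm | One hemoglobin test | Both tests (correlation 0.5 to 0.9) |
|---|---|---|
| 17 | 80.7% | 69–76% |
| 20 | 86.9% | 78–83% |
| 25 | 93.4% | 88–91% |

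Requiring GI success as well can only lower the last column. The amount cannot be computed, because the 10 per arm comes without an effect size, alpha or power.

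**Step 4: what the ANOVA tests.** Suppose once and twice daily are identical and controls are 0.5 higher (an assumption), with SD 1 and 20, 20 and 160 evaluable (200 × 0.8 = 160, assuming the same loss among controls). The overall mean lies 160 × 0.5/200 = 0.4 above the treated arms. The noncentrality is 40 × 0.4² + 160 × 0.1² = 6.4 + 1.6 = 8.0. Against the 5% critical value of F with 2 and 197 degrees of freedom (3.04), the ANOVA is significant about 71% of the time with no dosing effect. If controls are only 0.25 higher, the noncentrality is 2.0 and the figure is about 22%.

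**The case against.** The best defense is that the plan already treats efficacy and tolerability as two questions. They are separate aims, and GI has its own 10 per arm, below the 20 to 25 expected. This stands, and it rules out a stronger reading. A reader might infer that any one of the three primary outcomes suffices, which gives 11.7 to 13.6% with GI independent (14.3% if all are independent; 11.4 to 13.2% if GI correlates 0.3 with both hemoglobins). No passage says that one suffices, and the Hypothesis joins the outcomes with an *and*.

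That same *and* may mean that all must succeed. Then there is no inflation, and a reader might infer that the trial is underpowered. At the planned numbers the documents do not support this: power for both hemoglobin tests is near or above 80%. Withdrawn subjects are to be replaced, which may help. On the other side, losses from delivery elsewhere and transfer of care are not quantified. In any case, the Hypothesis is a prediction and is not written as a decision rule.

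Two further points are fair. The 7 to 9% counts both directions; falsely finding once daily better is 3.5 to 4.5% against 2.5% for one test, the same relative excess. The investigator also expects to use the results as preliminary data for funding, which weakens the case for strict control. Neither point says which hemoglobin decides Aim 1.

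**Conclusion.** The concern holds for Aim 1. Two hemoglobin results are primary, neither is designated as deciding, and the planned ANOVA does not isolate the randomized comparison. With efficacy and GI as separate aims, the error for Aim 1 is about 7 to 9% instead of 5%. This rests on two-arm tests and an assumed correlation of 0.9 to 0.5, with 9.75% as the figure under independence.

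Under an all-must-succeed rule, a material power shortfall would have to come from losses beyond 20% or from adding GI. The stated 17 per arm is correct for the single comparison it describes. The 71% in the ANOVA example depends on the assumed control difference and is an illustration, not a forecast. The inflation is moderate and depends on the reading. The missing rule does not, and it should be supplied before the data are analyzed.

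**What to change.** Name hemoglobin at admission for delivery, compared directly between the once daily and twice daily arms at two-sided 0.05, as the single primary outcome for Aim 1. Aim 1 and the 17-per-arm calculation support the two-arm contrast. They do not support a time point. The case for admission is that the planned regression takes maternal hemoglobin around delivery as its outcome, and that the admission sample is taken before delivery.

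Make post-partum day 1 hemoglobin secondary. Keep GI side effects as the Aim 2 outcome at its own 0.05. State that error is controlled within each aim and not across both.

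The cost is wording in the protocol and analysis plan, with no extra subjects or visits. Post-partum hemoglobin loses primary status. The chance of at least one false positive across the two aims remains up to 1 − 0.95² = 9.75% if the tests are independent, and the plan should say so. Keeping both hemoglobins as primary with alpha split to 0.025 each would instead lower the power of each test to 71.2%, 79.3% and 88.5% at 17, 20 and 25 per arm.

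### The only follow-up maternal hepcidin sample may be drawn before or after delivery, with no adjustment for draw time and no record of the last pill, which costs precision for Specific Aim 3

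*Combined protocol and SAP*

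**What the plan says.** Study Design gives two permitted times for the follow-up research tube: "The second will be drawn at the time of admission to the hospital for delivery or on post partum day 1". No rule chooses between them. The time follows clinical convenience, since the tube is taken "again generally at the time of an otherwise clinically indicated blood draw". On the assays the text says: "These samples will be stored for analysis of hepcidin and ferritin at the conclusion of the study". No other maternal follow-up sample is planned for hepcidin.

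Specific Aim 3 rests on this sample: "Determine the relationship between frequency of maternal iron administration and maternal hepcidin". The Summary treats hepcidin as tied to dosing. It reports a finding at a stated interval, "24 hours after a dose > 60mg, hepcidin increased", and adds "Hepcidin is increased with morning fasting dosing, which may affect the efficacy of twice daily dosing".

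Hemoglobin is handled differently. It is measured at both times as part of standard care: "the subject will have a hemoglobin repeated at the time of admission to labor and delivery and on post-partum day 1".

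The regression under Data Analysis controls for enrollment ferritin and hepcidin only. Its list of outcomes also leaves it unclear whether follow-up maternal hepcidin, as distinct from fetal hepcidin, is modelled at all. Pill-taking is checked by packs brought to clinic visits. The text does not ask for the time of the last pill before the delivery sample.

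**The concern.** Followed as written, the plan pools hepcidin values from two sampling conditions, one before delivery and one the day after, and treats them as one measurement. If hepcidin differs between the two, that difference enters the residual variance of the comparison between arms, and the planned model has no term to take it out.

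The interval from pill to sample is also uncontrolled and unrecorded. The treated arms differ only in whether the evening pill is iron or placebo, and the plan's own rationale describes hepcidin at a stated time after a dose. The interval from that pill to the draw is therefore relevant to Aim 3. If it is not recorded at the time, it cannot be recovered later.

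At stake is how informative the hepcidin comparison is. With about 20 evaluable women per arm, precision is already limited, and a null result would be harder to interpret.

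**Working it through.** **The plan's own figure.** The Power Analysis covers hemoglobin: difference 1 mg/dL, SD 1 mg/dL, alpha 0.05, 80% power, 17 per arm. A two-sided two-sample t-test needs 16.7 per arm, so 17, with power 80.7%. The figure reproduces, but it says nothing about hepcidin. No hepcidin power is stated.

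**Inputs from the documents.** 50 women randomised equally gives 25 per arm. A 20% loss leaves 25 × 0.80 = 20 per arm.

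**Assumptions, because the documents give no values:**
- the hepcidin SD at a fixed draw time is set to 1;
- the true once-versus-twice difference is 0.909 SD, back-solved as the difference that 20 per arm detects with 80% power (two-sided alpha 0.05);
- *D*, the hepcidin shift between admission and post-partum day 1, is 0.5, 1 or 2 SD and the same in both arms;
- *p*, the share drawn post-partum, is 0.5 or 0.1.

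**Formulas.** Variance with mixed draw times and no adjustment: V = 1 + p(1 − p)D². Effective number per arm: 20 / V. Standardised difference: 0.909 / √V. Power is then taken from the two-sample t-test with 20 per arm.

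| p | D (SD) | V | Effective n per arm | Power |
|---|---|---|---|---|
| any | 0 | 1.00 | 20 | 80% |
| 0.5 | 0.5 | 1 + 0.25 × 0.25 = 1.06 | 18.8 | 77.6% |
| 0.5 | 1 | 1 + 0.25 × 1 = 1.25 | 16 | 70.7% |
| 0.5 | 2 | 1 + 0.25 × 4 = 2.00 | 10 | 50.9% |
| 0.1 | 0.5 | 1 + 0.09 × 0.25 = 1.02 | 19.6 | 79.1% |
| 0.1 | 1 | 1 + 0.09 × 1 = 1.09 | 18.3 | 76.5% |
| 0.1 | 2 | 1 + 0.09 × 4 = 1.36 | 14.7 | 67.1% |

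**Bias or noise.** In this model the shift does not depend on arm, so the expected difference between arms is unchanged and only its variance grows. Chance imbalance remains possible. With 20 per arm and p = 0.5, the SD of the between-arm difference in the share drawn post-partum is √(2 × 0.25 / 20) = 0.158, about 16 percentage points.

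**Would dropping late samples help?** At p = 0.5, exclusion leaves 20 × 0.5 = 10 per arm and power of 49% for the same 0.909 SD. That is below the 71% obtained by leaving the samples mixed with a 1 SD shift.

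**Time since last pill.** The documents give no time course for hepcidin beyond the 24-hour observation, so no loss can be calculated for this part.

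**The case against.** The strongest reply is that Aim 3 is exploratory. The primary outcomes are hemoglobin and gastrointestinal side effects, the regression is described as exploring relationships, and no hepcidin power is claimed. The difference, the shift and the split used above are all assumed. A 50:50 split is the worst case for added variance. An admission draw is already standard, so most tubes may be taken then, and at 90:10 the loss is small unless the shift is large. The benchmark is also an unadjusted t-test, whereas the plan adjusts for enrollment hepcidin and ferritin. All of this stands, and it limits the weight of the point. It does not remove the gap: nothing in the text steers draws to admission, and neither planned covariate captures draw time.

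It is also fair to say that silence in the protocol is not proof that pill times go unrecorded. The case report forms are not among the documents and the design figure is not shown. The point is only that the text does not call for the record.

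A reader might infer four stronger claims, which the documents do not support:
- *The hepcidin signal fades within about a day.* The Summary reports it as present at 24 hours and gives no later course.
- *Delivery or its blood loss shifts hepcidin.* No section says so. The shift is an assumption.
- *Mixed timing pulls the difference between arms towards zero.* A shift common to both arms adds variance only. Attenuation would need an effect that wears off with time since the pill, for which the documents give no basis.
- *Aim 3 decides the follow-up studies.* Anticipated results and future directions makes that choice on whether once- or twice-daily dosing proves better, with only a general remark about using preliminary data.

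**Conclusion.** The concern holds in a limited form. The plan mixes two sampling conditions for its only follow-up maternal hepcidin value, has no term for draw time, and calls for no record of the last pill. The expected consequence is reduced precision for an exploratory aim. No systematic bias between the blinded, randomised arms is expected, and the hemoglobin outcomes are unaffected because hemoglobin is measured at both times.

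The size cannot be derived from the documents. The loss could be negligible (a 0.5 SD shift with few late draws) or substantial (a 2 SD shift with an even split, where 20 women per arm carry the information of 10). These figures rest on 20 evaluable women per arm, an assumed true difference of 0.91 SD, a shift common to both arms and no adjustment. The dosing-interval argument is documented for hepcidin, not for ferritin, and does not apply to the untreated controls. Mixed draw timing does apply to the controls.

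The change is worth making because it is cheap and the missing times cannot be reconstructed afterwards.

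**What to change.** 1. In Study Design, state that the research tube is taken with the standard admission blood draw in every woman, and on post-partum day 1 only when the admission tube was missed. Flag those late samples.
2. In Data Analysis, include draw time as a covariate in the maternal hepcidin regression. Keep flagged samples in the main analysis and exclude them only in a sensitivity analysis.
3. Record the clock time of the draw and of the last morning and evening pill.
4. Explore time since last pill among treated women only, and let its effect differ by arm, because the evening pill is placebo in one arm. A single common slope would be misspecified. Fixing the draw at admission does not standardise this interval, so the record is needed in either case.

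The cost is a sentence or two of protocol text, two or three form fields, and a few flagged late samples. No extra visit, blood draw or change to study treatment is involved.

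### GI side effects are a primary outcome, but the text describes no pre-treatment GI score and no baseline-adjusted analysis, so the once versus twice daily comparison is less precise than it could cheaply be

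*Combined protocol and SAP*

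**What the plan says.** The Summary gives GI symptoms primary status: "The primary outcomes will be hemoglobin concentration at the time of admission for delivery and post-partum and assessment of gastrointestinal side effects". The second Specific Aim asks whether once daily dosing has fewer side effects than twice daily dosing.

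On timing, the Study Design section makes two statements:

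- In general: "Subjects will be administered a validated questionnaire regarding gastrointestinal (GI) symptoms of iron usage at the time of follow up clinic visits".
- For the non-anemic controls: "Subjects without anemia will have weekly questionnaires regarding GI symptoms during otherwise scheduled prenatal visits".

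The mode is flexible: "This questionnaire will be administered via RedCap or via paper per patient preference". No number of questionnaires, interval or recall window is given.

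A baseline is planned for blood. Of the two research samples, "The first will be drawn at the time of enrollment, generally at the time of a clinically indicated blood draw for routine prenatal labs". The Data Analysis section uses the enrollment ferritin and hepcidin values as covariates. That regression ("Regression analysis will be used to explore the relationships of iron supplementation") concerns hemoglobin, hepcidin and ferritin, not GI symptoms. No analysis of GI symptoms is named there.

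The randomised contrast is narrow. All treated women take iron in the morning, and "The evening pill will be randomized to contain either ferrous sulfate 325mg or placebo". On blinding: "The subjects and investigators will be blinded to assignment".

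**The concern.** Pregnant women have GI complaints without taking iron. If symptoms are first recorded after the pills start, each woman's starting level stays in the outcome as noise. The contrast in the second aim is the effect of one additional iron pill on top of a pill that both arms take, measured in about 20 women per arm after losses, so avoidable noise matters. If the arms happen to differ at the start, the report could neither show it nor adjust for it. The plan already adjusts for baseline in its blood-marker regression, but not for this primary outcome.

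The second point concerns the controls. They are to be asked weekly, but at prenatal visits that are scheduled anyway, while the general statement refers to follow-up clinic visits. If the controls and the treated women complete different numbers of questionnaires, a summary that accumulates over questionnaires is not comparable between them.

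**Working it through.** **Inputs from the protocol (Power Analysis).** 50 women randomised, 25 per arm; 20% loss to follow-up; alpha 0.05; 80% power (stated for hemoglobin); 10 per arm for GI symptoms.

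**Assumptions.** Two-sided testing; 80% power for the GI comparison; baseline to follow-up correlation r between 0.3 and 0.7. The protocol gives none of these for GI symptoms.

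**1. The plan's own figures.** For hemoglobin (difference 1, SD 1), the two-sample t-test needs 16.7 per arm, rounded up to 17, so the stated 17 reproduces. The GI figure of 10 per arm cannot be reproduced, because no effect size, SD, event rate or power accompanies it. Worked backwards, 10 per arm at 80% power implies a difference of about 1.32 SD (t-test).

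**2. Completers.** 25 × (1 − 0.20) = 20 per arm.

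**3. Chance imbalance at the start.** The difference between two arm means, in SD units, has standard deviation √(2/n).

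- n = 20: √(2/20) = 0.32, so 95% of trials fall within ±1.96 × 0.316 = ±0.62 SD.
- n = 25: √(2/25) = 0.28.

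An imbalance of 0.62 SD would carry r × 0.62 into the follow-up comparison, for example 0.5 × 0.62 = 0.31 SD at r = 0.5. An unadjusted test already allows for this in its standard error. It is therefore the same loss as in step 4 seen from another side, not an additional bias.

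**4. Gain from adjustment.** ANCOVA multiplies the residual variance by 1 − r². The detectable difference with 20 per arm, 0.91 SD unadjusted, is multiplied by √(1 − r²), and the equivalent sample size is 20/(1 − r²). The one degree of freedom spent on the covariate is ignored.

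| r (assumed) | 1 − r² | Detectable difference (SD) | 20 per arm is worth | Power for 0.8 SD |
|---|---|---|---|---|
| no adjustment | 1.00 | 0.91 | 20 | 69% |
| 0.3 | 0.91 | 0.87 | 22 | 73% |
| 0.5 | 0.75 | 0.79 | 27 | 81% |
| 0.7 | 0.51 | 0.65 | 39 | 93% |

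**5. Questionnaire timing.** Set side by side, the two Study Design statements differ only between the controls (weekly, at scheduled visits) and subjects in general (follow-up clinic visits). Neither distinguishes the once daily arm from the twice daily arm. No arithmetic is attempted here, because the protocol gives neither the number of questionnaires nor the summary measure.

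**The case against.** The strongest objection is that a comparison based on follow-up alone is sound in a blinded, randomised trial. That is correct, and it rules out a stronger reading that a reader might infer: that pregnancy symptoms cannot be told apart from pill effects. For once versus twice daily, such symptoms are balanced in expectation by randomisation, and reporting is protected by the placebo evening pill. The stronger reading has force only for comparing treated women with the non-anemic controls, who are not randomised and take no pill, and for attributing symptoms to the morning iron that both arms take. Neither is the second aim.

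A reader might also infer that the randomised arms follow different questionnaire schedules, or that unequal counts bias the second aim. The text states no such difference between the arms. The control wording may simply be loose, since both statements tie the questionnaire to clinic visits. Any distortion from unequal counts would also depend on a cumulative summary that the plan does not specify, so its size cannot be computed from the documents.

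Three further objections carry some weight.

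- The gain depends on r, and at 0.3 it is small (0.91 to 0.87 SD).
- If the target really is about 1.32 SD, as 10 per arm implies, 20 completers per arm already give about 98% power without a baseline. But the protocol does not state that target, so it cannot be relied on to make the precision expendable.
- Excluding women with bowel disease, bowel surgery or current iron treatment narrows the spread of starting symptoms. It does not remove ordinary pregnancy symptoms.

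Finally, the study-design figure is not visible and may show a baseline questionnaire. The absence is established only for the readable text.

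**Conclusion.** The point holds as a cheap improvement, not as a threat to validity. For a primary outcome, the readable text gives no pre-treatment score and no baseline-adjusted analysis. For once versus twice daily, the cost is lost precision and no check on chance imbalance. The variance that adjustment would remove is 9% at r = 0.3, 25% at r = 0.5 and 49% at r = 0.7. These sizes rest on an assumed correlation, 20 completers per arm, two-sided 0.05 and 80% power. They would matter little if the true difference is as large as the stated 10 per arm implies, and more if it is nearer 0.8 SD.

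The mismatch in timing wording is a separate and smaller matter. It bears only on comparisons of GI symptoms with the non-randomised controls.

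**What to change.** 1. In Study Design, add the same GI questionnaire at enrollment, before the first pill.
2. Replace the two timing statements with one schedule and one recall window for all groups, delivered by the RedCap or paper route already planned.
3. In Data Analysis, add a sentence: once versus twice daily will be compared on each woman's mean follow-up GI score, by ANCOVA adjusted for her baseline score.
4. If the study-design figure already shows a baseline questionnaire, bring the text into line with it and use that score as the covariate.

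The cost is one extra questionnaire per woman at a visit that already takes place, a schedule setting in RedCap and one sentence of analysis text. The change has to be in place before a woman starts treatment, since a pre-pill score cannot be obtained afterwards.
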